### **9.2.2 Other regulatory approvals**

Before sites begin to enrol participants into the study, HRA approval will be sought for each NHS site. The Chief Investigator/Principal Investigator or designee will ensure that appropriate approvals from participating organisations are in place (HRA approval and site capacity and capability approval).

The sponsor and the University of Manchester regulatory approvals advisor have reviewed and assessed the study.

The app is not a medical device as described in the MHRA decision tool. Whether an app (or other piece of software) is a medical device depends on the intended purpose. The purpose of the CONNECT app is to collect data. It is not intended to prevent or treat a medical condition.

### **9.2.3. Amendments**

When an amendment to the study is needed, the Chief Investigator or designee will ensure that the current procedure for obtaining approval for amendments are followed.

Once approved, the Chief Investigator or designee will notify sites of amendments and will work with sites (R&D departments at NHS sites as well as the study delivery team) so they can put the necessary arrangements in place to implement the amendment to confirm their support for the study as amended.

The amended version of the study protocol (and any other amended documents) will be added to the study site file to ensure that the most up to date approved documentation is used at all sites.

## **9.3 Peer review**

The CONNECT study has undergone rigorous scientific review as part of the Wellcome Trust Innovation Flagship funding scheme process. The Wellcome Trust has reviewed multiple iterations of the project and convened an international expert panel interview with members from the study team. All members of the study team have reviewed and approved the protocol, as well as the CONNECT advisory groups, which includes experts by experience, technical platform and data security experts, analytics, clinical pathways and regulation. Senior academics from The University of Manchester, independent to the study team, have also reviewed the project, as well as an IG expert at The University of Manchester. The application has been peer reviewed, and approved by, the funder.

Important documents such as the Safeguarding and Distress Management Protocol, protocol, and participant facing documents have been independently reviewed by lived experience colleagues.

#### **9.4 Public and Patient Involvement (PPI)**

People with lived experience of psychosis have been involved in the study design and will be involved in study management, analysis and dissemination. *A study co-investigator with lived experience of psychosis ([name], McPin Foundation) will lead the study patient and public involvement (PPI) group and is a member of the Project Management Group and Project Board. We have three levels of PPI:*

- i. Involvement Network (IN), who will be invited to undertake ad hoc, bespoke work on the study as needed;*
- ii. Lived Experience Advisory Panel (LEAP), which is smaller group of lived experience members from the Involvement Network; and*
- iii. Expert Reference Group (ERG) comprising a range of stakeholders and experts who will meet throughout the programme of work to advise on project design, management, dissemination.*

Specific examples of PPI input at each stage include:

- Study design: qualitative interview topic guide, participant information sheet, consent form, research protocol, study procedures, newsletter, engagement strategy, IRAS form and other ethics documents.
- Management: PPI contributors will meet during the study to advise on study management. e.g., recruitment strategy.
- Analysis of results: members with lived experience of psychosis will assist in the qualitative analysis and assessment of predictor variables, supported by colleagues from the McPin Foundation.
- Dissemination: PPI contributors will co-produce a lay summary of the results and present at conferences and other meetings as far as is possible.

Our PPI contributors have already made a significant contribution to the study, including reviewing the information sheet, consent form, study protocol, ethics documents and IRAS form, ethical consideration of the study and elements of the study design and processes, including risk and safeguarding.

PPI contributors will be financially reimbursed for time spent contributing to the research, in line with NIHR guidelines. PPI contributors will be listed collectively or individually in publications as authors wherever possible. An acknowledgement for PPI contributions will be given in academic and other publications.

#### **9.5 Protocol compliance**

Accidental protocol deviations can happen at any time. They will be adequately documented and reported to the Chief Investigator and Sponsor immediately. Deviations from the protocol that recur frequently are not acceptable, will require immediate action, and could potentially be classified as a serious breach. The sponsor will be notified immediately of any case where a serious breach (i.e. a breach which is likely to effect to a significant degree the safety or physical or mental integrity of the participants of the study; or the scientific value of the study) occurs.

## **9.6 Financial and other competing interests for the chief investigator, PIs at each site and committee members for the overall trial management**

No potential competing interest was reported by [name], [name], [name], [name], [name], [name], [name], [name], [name] and our PPI partner McPin.

[name], [name], and [name] are Directors and shareholders of CareLoop Health Ltd, a University of Manchester startup company which develops and markets digital therapeutics for schizophrenia. CareLoop Health Ltd owns the commercial rights to the active symptom monitoring app and platform used in this study.

[name] was Chief Investigator of the NIHR funded EMPOWER trial which has informed the design of the CONNECT study including active data capture, fear of recurrence assessment and relapse definition.

[name] is the Sussex lead for Akrivia Health which runs the Clinical Record Interactive Search (CRIS) data systems across the UK. There are no financial links.

[name] holds a research grant from Takeda Pharmaceuticals to develop novel drug targets using genetic data.

## **9.7 Indemnity**

The University of Manchester will arrange insurance for research involving human subjects that provides cover for legal liabilities arising from its actions or those of its staff or supervised students in relation to study management, design and conduct (subject to policy terms and conditions).

For protocol authors with substantive NHS employment contracts, indemnity in relation to study design will be provided through NHS schemes. Where the participants are NHS patients, indemnity in relation to study conduct will be provided through the NHS schemes or through professional indemnity.

Non NHS sites will have their own insurance in place to cover indemnity in relation to the conduct of the study by their employees.

## **9.8 Adverse events**

Details of recording and reporting of all adverse events will be contained in a SOP for Adverse Events. To comply with Standards for Good Clinical Practice (GCP), it is important that all researchers are aware of the different definitions related to adverse events in research and how to record, report and review each of these specific occurrences. Adverse events are reportable from the time of study enrolment, defined as the time at which, following recruitment, a participant signs and dates the informed consent form.

An adverse event (AE) is defined by the HRA as any untoward occurrence or worsening of an unintended sign, symptoms or disease that occurs during participation, regardless of any relation to participation. AEs will be recorded and initially assessed for severity and seriousness by site researchers. Level of severity will be categorised as mild, moderate and severe, which reflect the impact of the event on the person at the time. There is a distinction between 'severe' and 'serious'. Seriousness is the criterion for defining regulatory reporting obligations. An adverse event will be classified as serious if it results in: death, injury or permanent impairment to a body structure or body function; serious deterioration in the health of the subject; or foetal distress, foetal death, or a

congenital abnormality or birth defect. However, in this study any AE rated as 'severe' will automatically be classified as a SAE and will be reported immediately to the PI. Urgent actions concerning participant and staff safety, communication with others, and clinical care will be immediately addressed by the PI. SAEs will be further reviewed for unexpectedness and relatedness to the investigational device and/or study procedures by the PI.

If an SAE is thought to be related to participation in the study, it will be reported to the Research Ethics Committee within 15 days using the National Research Ethics Service template, signed by the chief investigator. Other AEs will be reported in the Annual Progress Report to the ethics committee and copied to the sponsor.

An Adverse Event Log file will be created to systematically record occurrences, with reference to an a priori defined list of anticipated and unanticipated adverse events.

All deaths will be reported to the sponsor within 24 hours irrespective of whether the death is related to taking part in the study or an unrelated event.

### ***9.8.1 Exemptions to adverse event reporting***

Hospitalisation for elective surgery, a planned hospital admission for a pre-existing condition, or a planned change in medication under supervision without deterioration in health, are not considered to be SAEs and are excluded from SAE reporting (i.e. an Adverse Event Report Form is not required).

The following adverse reactions are expected (anticipated) and do not need an AE Form completed (and therefore do not require reporting):

- Transient / short-lived increased awareness of thoughts resulting in negative emotions (e.g. some distress, tearful) during/on completing an assessment, interview or while using the CONNECT app;
- Irritation/skin rash with wearable strap;
- Some discomfort in having sleep or location data (for example) collected;
- Minor irritation or annoyance reported with app alerts/notifications.

Untoward and unintended responses will therefore NOT include these specified reactions.

Technical glitches such as periodic network outage, other minor technical hitches with the apps, phone loss, phone theft and/or a participant selling the phone are NOT counted as AEs but will be systematically logged in a study spreadsheet. If this does, however, result in a decline in mental state (e.g. phone theft as a result of physical assault) then this will be recorded as an adverse event and the phone theft coded as the trigger (as opposed to the AE itself).

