A systematic review of studies (Chivilgina, et al., 2020) identified four PSM studies (we identified a further five), with usage ranging from 5 to 365 days in sample sizes ranging from 5 to 62 participants. Acceptability is reported in two studies, which showed PSM was largely acceptable; although, 20% participants reported privacy concerns and 20% felt upset by it. More specifically, Barnett and colleagues (Barnett, et al., 2018) followed 17 people with lived experience of psychosis using the Beiwe PSM app installed on their smartphone for up to 3 months and identified anomalies in mobility patterns and social behaviour in the 2-weeks prior to relapse. This was also observed in a slightly larger ( $n = 60$ ) study by members of the same group using a neural network approach (Adler, et al., 2020). In another study, Ben-Zeev and colleagues (Ben-Zeev, et al., 2017) noted sensor data changes including physical activity, geolocation, phone unlock duration, and speech frequency and duration in psychosis participants prior to relapse. Wisniewski and colleagues (Wisniewski, et al., 2019), in a case series, also noted high variability in behavioural patterns observed through PSM between individuals, suggesting a stratified approach (using individualised digital phenotype mechanisms) to identify individuals entering a clinically high-risk state. Cella and colleagues (Cella, et al., 2018) found that wearable technologies were acceptable and reliable for measuring autonomic activity (heart rate variability) in 30 people with lived experience of schizophrenia. Members of our team also conducted initial experiments to identify daily activities relevant for assessing social functioning from Global Positioning System (GPS) data, using a publicly available annotated digital map (OpenStreetMap). In 21 people with psychosis (Fraccaro, et al., 2019), we were able to predict daily activities reflective of

social functioning with a precision of 0.75 and a recall of 0.60. PSM studies have shown that most people with lived experience of psychosis are comfortable, able and willing to use wearable devices to monitor outcomes in their daily life (Cella, et al., 2019), with emerging evidence supporting identification of an impending relapse through changes in passively collected behavioural data. However, robust safety data is needed to understand the utility of this approach more clearly.

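### The strap-rash exemption in section 9.8.1 has no severity limit and conflicts with the section 9.8 rule that any severe event is an SAE; no precedence is stated.

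*Protocol*

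**What the plan says.** Protocol section 9.8 sets the general rule. It defines an adverse event broadly, whatever its relation to taking part. Site researchers record each event and assess its severity (mild, moderate or severe) and its seriousness. The section separates severe from serious, then links them for this study: an adverse event rated severe "will automatically be classified as a SAE and will be reported immediately to the PI". The PI reviews SAEs for unexpectedness and for relatedness to the device or study procedures. An SAE thought to be related to participation goes to the ethics committee within 15 days.

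Section 9.8.1 sets the exemptions. Four expected reactions "do not need an AE Form completed (and therefore do not require reporting"). They are:

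- "Transient / short-lived increased awareness of thoughts resulting in negative emotions", during or after an assessment or interview, or while using the app;
- "Irritation/skin rash with wearable strap";
- "Some discomfort in having sleep or location data (for example) collected";
- "Minor irritation or annoyance reported with app alerts/notifications".

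It then adds: "Untoward and unintended responses will therefore NOT include these specified reactions".

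**The concern.** The two sections give opposite instructions for one kind of event. If a participant has a strap reaction that a researcher would rate severe, 9.8 calls for immediate reporting as an SAE, while 9.8.1 waives the form and the report. Nothing says which comes first.

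What is at stake is the safety reporting route. The wearable is meant to be worn 24 hours a day (section 9.1.2) for 12 months (section 5.8.2), and strap irritation or rash is the only physical reaction on the exempt list. By its description it is linked to the study device. If severe, it is therefore the kind of event that the relatedness review and the 15-day ethics report are meant to catch. The Research Steering Group, which monitors adverse events (section vi), would depend on the same route.

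**Working it through.** There is no figure to reproduce and no arithmetic applies. The check sets the two sections side by side.

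**1. Is the strap item really without a limit?** The four listed reactions compare as follows.

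| Exempt reaction | Limiting word |
|---|---|
| Negative emotions from awareness of thoughts | Transient / short-lived |
| Strap irritation or rash | none |
| Discomfort at sleep or location data being collected | Some |
| Irritation or annoyance with alerts | Minor |

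Three of the four carry a limit. The strap item does not.

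**2. Does another clause return a severe strap reaction to reporting?** Section 9.8.1 limits some of its other exemptions. A planned medication change is exempt only if health has not deteriorated. Technical faults and phone loss or theft are not adverse events, but they come back into reporting if they lead to a decline in mental state. No such clause applies to the four listed reactions.

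**3. What happens to a severe strap reaction under each section?**

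| Step | Under 9.8 | Under 9.8.1 |
|---|---|---|
| Counts as an untoward event | yes | no |
| Adverse event form | the ordinary route | not needed |
| Severity and seriousness rating | by the site researcher | no step requires one |
| Classed as an SAE | automatically, if rated severe | not reached |
| Reported to the PI | immediately | not required |
| Relatedness review and possible ethics report | follows from SAE status | not reached |

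**4. Can the sections be read together without conflict?** There are two ways to try.

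- *9.8.1 is only a waiver of paperwork.* The reaction is still an adverse event and still rated. A severe one must then be reported immediately under 9.8 and need not be reported under 9.8.1, which is a direct contradiction.
- *9.8.1 narrows the definition.* The reaction is never an adverse event, so it is never rated and the severe-event rule is never triggered. The formal contradiction goes, but the gap stays: how bad the rash is never comes into question.

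Neither reading gives a severe strap reaction a clear route. The schedules of assessments in Appendices 1 and 2 prompt researchers to record adverse events throughout follow-up, so the chance to notice a rash exists. On the second reading, however, what is noticed would not count as an adverse event.

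**The case against.** The best defence is context. The item sits among reactions worded as mild, in a list of expected effects of commercial devices that the protocol calls very low risk. A sensible researcher would take it to mean ordinary strap irritation and would report a severe rash anyway. That is probably what the authors intended, and it bears on how often the gap would matter. It does not settle which rule governs, because the limit the neighbouring items carry is missing here.

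A reader might also infer more than the protocol supports.

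- *That a severe strap reaction would certainly go unrecorded, or that exempt reactions are counted nowhere.* Section 9.8.1 removes the form and the report; it does not say that all recording stops. Section 9.8 sets up an Adverse Event Log that refers to a list of anticipated as well as unanticipated events, and it leaves details of recording and reporting to an SOP that is not shown. Either might capture the reaction. What can be said is that it could go unreported.
- *That serious device harm in general is exempt.* Section 9.8 keeps severe and serious apart, and 9.8.1 covers only irritation or rash with the strap. Other device injuries stay reportable.
- *That the size can be taken from section 1.4*, where, in earlier passive-monitoring studies, "20% participants reported privacy concerns and 20% felt upset by it". That concerns feelings about passive sensing. It says nothing about strap rash or its severity, so scaling it to the 1100 participants would not measure this gap.
- *That the acceptability outcomes or the device comparison are damaged.* Acceptability comes from collected data, satisfaction and usability questionnaires and interviews, not from adverse event forms. The nested wearable comparison was analysed in January 2025 and its device decisions have been made.

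**Conclusion.** The point holds as a conflict between two stated rules. Section 9.8.1 exempts strap irritation or rash at any severity and takes it out of the definition of untoward responses; section 9.8 makes any event rated severe an SAE for immediate report. For a severe strap reaction the protocol gives no precedence, so the reaction could go unreported, with no adverse event form and no severity or seriousness rating.

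The number of participants affected cannot be derived, because the protocol gives no rate of strap reactions or of severe ones. With low-risk consumer devices it may be small. The conclusion rests on the wording of the two sections alone and assumes that the unseen SOP does not already settle precedence. Even if it does, the protocol text still needs to agree with it. The primary analysis and the sample size are unaffected. The point is worth correcting because it concerns participant safety and the correction is nearly free.

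**What to change.** Reconcile the two sections with one sentence in 9.8.1: the exemptions listed there do not override section 9.8, and a listed reaction that is severe or meets a seriousness criterion is recorded, rated and reported under 9.8. Check that the adverse event SOP says the same.

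Ordinary strap irritation stays exempt. There is no need to confine the exemption to mild reactions or to add tallies by device; both go beyond the conflict. The cost is one sentence in the next amendment and an occasional extra adverse event form.

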## **10 Dissemination Policy**

### **10.1 Overview**

It is intended that the results of the study will be reported and disseminated at national and international conferences and in peer-reviewed scientific journals. They will be made available to participants and clinical teams in an accessible format, and on the study website. They will also be accessible in print and digital media and presented at stakeholder events. The data arising from the study will be owned by UoM. On completion of the study, the data will be analysed and tabulated, and a final study report prepared.

We will organise a number of events for stakeholders across sites to identify and share key learning experiences arising from the study and to facilitate scoping and engagement of stakeholders participating in the study.

## **10.2 Authorship eligibility guidelines**

No professional writers will be involved in the production of the final project report and other peer-reviewed publications that will result from the research activities conducted as part of the project. Determination of individuals to be involved in the preparation and authorship of publications arising from the study will be based on the International Committee of Medical Journal Editor (ICMJE) guidelines on authorship (<http://www.icmje.org>).

Authorship will be considered separately for each publication arising from the study. In line with ICMJE guidelines, authorship of each publication will be based on the following criteria:

substantial contribution to: (a) the conception or design of the work; or (b) the acquisition, analysis, or interpretation of data for the work and (c) drafting the work or revising it critically for important intellectual content and (d) final approval of the version to be published and (e) agreement to be accountable for all aspects of the work in ensuring that questions relating to the accuracy or integrity of any part of the work are appropriately investigated and resolved.

Examples of activities contributing to authorship are as follows.

- Conception and design would include development of original ideas behind project, and research design (e.g., deciding inclusion criteria, conditions, measures, overall methodology).
- Acquisition of data includes development of project procedures (e.g., recruitment procedures, assessment procedures and materials, randomisation procedures, risk management procedures, decision making re ethics submissions and amendments). Further clarification regarding procedural activities is included below.
- Analysis, interpretation and write-up would include intellectual contributions to the analysis and interpretation of results.

The individuals involved in the write-up of a publication will usually be those who have been involved in the work (i.e., in conception, design, acquisition of data and/or analysis). An exception to this will be where an additional author has a particular role to play in joining the team to facilitate the interpretation of findings. However, their role would need to amount to a substantial contribution to the overall manuscript to justify authorship.

When a dataset is reused for publications in addition to the main planned paper(s), the background work for design of the original project and contributions to project management and data acquisition should be factored into those publications. However, background contributions need to be weighted in terms of how much they influence the findings of these publications. This will depend upon how extensive and novel the new conceptualisations and analyses that have been conducted are. In most cases, it is expected that only those very heavily involved in the original project would have background contributions that would carry over to a new publication as 'substantial' solely on that basis.

Every effort will be made to include people with lived experience from the study LEAP and Involvement Network as co-authors on all publications. In every case, an acknowledgement for the Patient and Public Involvement contributions to the study will be made.

